### **Adherence and Treatment Satisfaction Outcomes:**

**Self-Reported Adherence and Barriers:** Caregivers and children will answer standardized questions related to adherence and adherence barriers to taking SGAs, MET (if applicable), and LIFE. Information on missed and partial doses of each medication in the past week will be ascertained. Questions prefaced by non-judgmental language that normalizes non-adherence to treatment will be used. A time period of one week will be used to maximize respondent recall and minimize memory decay.

**MEMS®6 TrackCap/SimpleMed PillBox:** The Medication Event Monitoring Systems (MEMS) [AARDEX Corporation] and the SimpleMED PillBox are electronic monitoring systems that measure the dosing histories of oral medications. They will be used to monitor adherence to SGAs or MET in a sub-sample of 300 patients at a subset of sites. They consist of a standard plastic vial or box with a threaded opening and a closure for the vial that contains a micro-electronic circuit to register the dates and times the bottle/pillbox is opened and closed. Data from the MEMS TrackCap will be downloaded at each study visit. Patients randomized at an inpatient site to MEMS monitoring will only receive this monitoring if they are scheduled to be followed at an outpatient site that was selected for MEMS monitoring; otherwise, the MEMS aspect of the randomization should be disregarded.

**Treatment Acceptability:** A single-item 5-category Likert-type patient report of satisfaction with psychotropic medication regimen (0=not at all satisfied to 4=very satisfied).

**International Physical Activity Questionnaires (IPAQ):** The IPAQ is an instrument for cross-national monitoring of physical activity and inactivity with good reliability and validity for monitoring population levels of physical activity in diverse settings to assess adherence to LIFE physical activity recommendations.

We will also assess food choices and eating habits using questions selected from the Healthworks Nutrition Screener, Satiety and Food Responsiveness using items from the Child Eating Behavior Questionnaire, and Uncontrolled Eating and Cognitive Restraint using items from the 3-factor Eating Questionnaire.

**Psychiatric Outcome Measures:**

**PROMIS (Patient-Reported Outcomes Measurement Information System)** measures undergo a standardized, extensive measure development process which includes literature review, expert meetings, qualitative interviews with families, item development, cognitive testing of the item content, confirmatory factor analyses to establish construct validity, and item response theory to establish psychometric properties. We will use items from the validated short-form assessments of Anxiety, Depression and Anger as well as Global Health and Peer Relationships (the latter two are HRQoL instruments; see next section).

**PROMIS Anxiety Short Form:** focuses on fear (e.g., fearfulness), anxious misery (e.g., worry), and hyperarousal (e.g., nervousness). Marginal Cronbach's  $\alpha > 0.85$

**PROMIS Depression Short Form:** focuses on negative mood (e.g., sadness), anhedonia (e.g., loss of interest), negative views of the self (e.g., worthlessness, low self-esteem), and negative social cognition (e.g., loneliness, interpersonal alienation). Marginal Cronbach's  $\alpha > 0.85$

**PROMIS Anger Short Form:** assesses angry moods (e.g., irritability and reactivity) and aggression (verbal and physical). Marginal Cronbach's  $\alpha > 0.80$

**Clinical Global Impressions Scale-Severity (CGI-S):** Single-item assessments of symptom severity. Severity is rated from 1 (not at all ill) to 7 (among the most severely ill patients).

**Young Mania Rating Scale (YMRS):** 11-item clinician-rated instrument that assesses symptoms of mania.

**Children's Depression Rating Scale (CDRS)-Revised selected items:** a clinician-rated scale used for assessing severity of depression and change in depressive symptoms.

**Quality of Life (QoL) and Functional Outcomes:** We will ask patients and caregivers the number of days that they missed from school and work, respectively, in the last month and will use items from the following scales:

**PROMIS Global Health:** assesses physical, mental, and social health. Cronbach's  $\alpha=0.88$ .

**PROMIS Peer Relationships:** measures understanding and communication; companionship; and quality, reciprocity, and size of patients' social network Cronbach's  $\alpha> 0.80$ .

**Children's Global Assessment Scale (CGAS):** A single-item index of overall functional capacity. Scores range from 1 (indicating severe impairment) to 100 (indicating superior functioning).

**Sizing Me Up & Sizing Them Up:** self-report and parent-proxy measures of obesity-specific HRQoL for youth, with subscales measuring Emotional, Physical and School Functioning, Teasing/ Marginalization, Positive Social Attributes, Mealtime Challenges, and Social Distress/Avoidance, and a Total QoL score. Excellent documented internal consistency, test-retest reliability and convergent validity.

Body Weight, Image and Self-esteem Evaluation (B-WISE®): scale designed to capture and quantify weight satisfaction, ability to control food intake, self-esteem and other the psychosocial consequences of weight gain, scored on a 3-point Likert scale from 1 (never)-3 (all the time), Cronbach's  $\alpha=0.79$ .

Caregiver Strain Questionnaire-Short Form 7 (CGSQ-SF7): Routine assessment of objective and subjective internalized caregiver strain, scored on a 5-point Likert scale from 1 (not at all)-5 (very much a problem), with good validity and reliability.

#### **Laboratory Measures:**

Site staff will collect and report any lab results that are obtained as part of the patient's clinical care. Laboratory tests will be suggested according to clinical practice guidelines, but will not be required for patients enrolled in MOBILITY, with the exception of a pregnancy test for all girls who have reached menarche and who are randomized to metformin. Additionally, since patients receive their treatment at mental health treatment facilities throughout the country and MOBILITY is a pragmatic study, patients may have laboratory tests performed at any laboratory facility that they typically would as part of their routine clinical care. We will collect the results of the laboratory tests once they are available in medical records. Therefore, we will not require CLIA certificates or other regulatory documents for each laboratory facility. Table 2 (at intervals that reflect standard clinical care) indicates the recommended lab measures according to practice guidelines.

#### **Other outcome measures:**

Patient Health Questionnaire-9 (Item 9): Assesses current suicidality; 0 (not at all), 3 (nearly every day) scale.

Zucker Hillside Side Effects Form: Assesses intensity (1=not present, 4=severe) of adverse events in five domains (behavioral, neurological, cardiovascular, autonomic, GI side effects). Open ended AE (adverse event) questions at every visit.

### **STUDY SCHEDULE AND TREATMENT**

Since MOBILITY is a pragmatic study, we will collect the above information, when possible, and in conjunction with patients' clinical visits. We will allow for data collection approximately monthly for the first three months, followed by every three months thereafter, for a total duration of 24 months. However, these visits and timeline are just guidelines. Data will be collected through information acquired during clinical visits. There is no minimum number of visits required for patients to continue to participate in MOBILITY and have their data collected. However, sites should not schedule patient appointments exclusively to conduct study specific visits or procedures. Therefore, it is anticipated that **not all study visits or procedures will be completed for every patient. However, we will emphasize the importance of collecting Month 6 and 24 data since those are primary outcomes.** Labs tests that are recommended in the Schedule of Events are based upon standard clinical practice guidelines, but will not be required for continuation in the study.

Each site will have a copy of the MOBILITY Projected Visit Dates Spreadsheet (also found on the website: MOBILITYstudy.org). The site coordinator will enter the patient's baseline visit date where indicated, and the recommended visit schedules will auto-populate. However, once patients are randomized at baseline, MOBILITY is primarily an observational pragmatic study, therefore, data will be collected only at clinical appointments.

**Screening/Baseline Procedures:** At screening and following informed consent/assent and review of initial study criteria, we will obtain demographic and clinical information as follows:

Demographic and Clinical Characteristics: Site staff will record patients' date of birth, sex, type of insurance, contact information, and prior type and duration of psychiatric treatments. Patients will report current daily nicotine intake (packs/day) and whether they currently use other drugs (checking all that apply from a list of common drugs). Data on treatments and substance use will also be collected at six-

month intervals.

Screening laboratory tests recommended include renal and hepatic function tests, electrolytes, CBC and thyroid stimulating hormone (TSH), as per Table 2. However, we will collect any results of labs performed within the last six months, if available. The only mandatory test for screening will be a pregnancy test in girls of menarche.

Every attempt will be made to encourage clinicians to obtain laboratory testing prior to starting metformin, however, patients who have not had baseline labs will continue to be followed in MOBILITY.

Kiddie-SADS-Present and Lifetime (K-SADS-PL 2013): After discussion with our patient/parent partners and site clinicians, we determined that the appropriate study population is all patients who receive a clinical diagnosis of a BSD, as these patients will typically receive SGA treatment regardless of whether they meet full DSM criteria. However, it was decided that using a structured research interview would provide an opportunity to examine concordance of clinical and research diagnoses and to assess HTE (i.e., do youth with a research diagnosis respond to MET differently than those with only a clinical diagnosis because risk for overweight/obesity and metabolic disorder may be higher for those with a research BSD diagnosis). Therefore, BSD diagnoses will be confirmed with the mood modules of the K-SADS-PL, a semi-structured diagnostic interview with established test-retest reliability. (Interviewers will be trained by qualified personnel. Trained staff at the respective coordinating centers who are not associated with the clinical sites will administer the interview separately to guardians and patients, if > 12 years old). Based on feedback from the clinical sites, we determined that having their staff administer the K-SADS-PL might create diagnostic confusion, therefore, we will develop a mechanism that clinicians will be provided with the K-SADS-PL diagnoses after participants have reached Month 6 of study participation.

Table 1. Metformin (MET) Titration		
	<50kg AM/PM	≥50kg AM/PM
Week 1	0/500mg	0/500mg
Week 2	0/500mg	0/500mg
Week 3	500/500mg	500/500mg
Week 4	500/500mg	500/500mg
Week 5	500/1000mg	500/1000mg
Week 6	500/1000mg	500/1000mg
Week 7	500/1000mg	1000/1000mg
Week 8	500/1000mg	1000/1000mg

Type and duration of current/prior SGA treatment and weight gain during SGA treatment: Prior data suggest that the effect of MET may depend on the extent of weight gain during SGA treatment prior to study entry. Site personnel will document weight and height prior to any SGA treatment, specific SGAs received and duration of treatment with each (i.e., by obtaining medical records). For *a priori* analyses of potential heterogeneity of treatment effect (HTE), we will then distinguish SGA-naïve patients (no current or prior SGA treatment as of baseline visit) versus those with any current or prior SGA treatment. Within the latter group, we will compute change in BMI z-score from the start of SGA treatment until baseline and perform HTE analyses to determine whether MET effectiveness varies based on the duration of SGA treatment and/or amount of excess (relative to normal development) weight gained during treatment.

Classification system for psychotropic treatments: We anticipate substantial variation in the specific psychotropic medication regimens prescribed at baseline, and that these treatments will vary over time. SGAs may be prescribed singly or in combination at varying doses, and concomitant treatment with antidepressants, non-SGA mood stabilizers (e.g., divalproex and lithium) and/or stimulants (e.g., for the subset of patients with co-morbid ADHD) will also be common. For our *a priori* analyses of potential HTE depending on pharmacologic treatments other than MET, we have reduced this large set of options to three groups based on available data regarding their weight effects. Our data will provide considerable additional observational evidence about the impact of specific regimens, and we will conduct detailed analyses that may suggest useful *post-hoc* alternative classifications. Our survey data indicate that

risperidone, aripiprazole, and quetiapine will be the three most common SGAs prescribed.

- (1) Mild to Moderate Risk of Weight Gain: Monotherapy with lurasidone, ziprasidone, or aripiprazole.
- (2) High Risk of Weight Gain: Monotherapy with asenapine, iloperidone, paliperidone, quetiapine or risperidone. SGA-naïve patients receiving monotherapy with a group (1) SGA and patients prescribed divalproex or lithium plus a group (1) SGA will be assigned to this group.
- (3) Severe Risk of Weight Gain: Monotherapy with clozapine or olanzapine. SGA-naïve patients receiving monotherapy with a group (2) SGA and patients prescribed divalproex or lithium plus a group (2) SGA will be assigned to this group.

Note that we have not incorporated dose effects because dose-dependent weight gain has not been consistently demonstrated for most SGAs. We will examine association of dose and dose adjustments with weight change and other outcomes, though exploratory analyses of such observational relationships will require careful consideration of confounding factors.

**(See Next Page)**

**Table 2. Schedule of Events.**

The Table of Events is an approximation for when routine clinic visits might occur. In order to adhere to the pragmatic nature of the study, data will only be collected during the patient's regularly scheduled clinical visits and a participant should not be brought in exclusively to conduct study specific visits. No specific study labs will be mandated for study participation, with the exception noted above (i.e., pregnancy test) The lab tests noted in the Schedule of Events are suggested in accordance with clinical practice guidelines for patients receiving SGAs.

Measures	Visit (Approximate Months)										
	SCREEN/ BASELINE	1	2	3	6	9	12	15	18	21	24
Demographics & Clinical Characteristics (P, Y)	X										
Structured Diagnostic Assessment (K-SADS) a (C)	X										
Medication List (C)	X	X	X	X	X	X	X	X	X	X	X
Weight/Metabolic											
Body Mass Index [height and weight] (C)	X	X	X	X	X	X	X	X	X	X	X
Recommended Metabolic Labs [insulin, lipid profile, glucose, hemoglobin A1C] (C)	X b,d, e				X		X		X		X
Treatment Satisfaction											
Treatment Acceptability Questionnaire (Y)	X	X	X	X	X	X	X	X	X	X	X
Adherence											
Adapted Adherence Measure (P & Y)	X	X	X	X	X	X	X	X	X	X	X
International Physical Activity Questionnaire (P & Y)	X	X	X	X	X	X	X	X	X	X	X
Nutrition, Satiety, and Appetite Measures (P & Y)	X	X	X	X	X	X	X	X	X	X	X
MEMs Cap/ SimpleMed Pillbox Upload [300 patient subset] (C)		X	X	X	X	X	X	X	X	X	X
Mood/Anxiety											
PROMIS c Anxiety Short Form (P & Y)	X				X						X
PROMIS c Depression Short Form (P & Y)	X	X	X	X	X	X	X	X	X	X	X
PROMIS c Anger Short Form (P & Y)	X				X						X
Children's Depression-Revised/Selected Items (C)	X				X						X
Young Mania Rating Scale (C)	X	X	X	X	X	X	X	X	X	X	X
Clinical Global Impression-Severity (C)	X	X	X	X	X	X	X	X	X	X	X
Quality of Life (Weight & General)											
Body Weight, Image & Self-Esteem Evaluation, B-WISE (Y)	X				X						X

"Sizing Me Up"/"Sizing Them Up" (P & Y)	X				X						X
Height Weight Self for Viewpoint-Items 5 & 6 (wt. acceptability) (Y)	X	X	X	X	X	X	X	X	X	X	X
PROMIS c Pediatric Peer Relationships- Short Form (P & Y)	X				X						X
PROMIS c Global Health Scale (P &	X	X	X	X	X	X	X	X	X	X	X
Clinical Global Assessment Scale (C)	X	X	X	X	X	X	X	X	X	X	X
Number of School/Work Days Missed [past 30 days] (Y & P)	X	X	X	X	X	X	X	X	X	X	X
Caregiver Strain Questionnaire (P)	X	X	X	X	X	X	X	X	X	X	X
Other recommended measures											
Vital Signs [blood pressure, heart rate] (C)	X	X	X	X	X	X	X	X	X	X	X
Other recommended laboratory measures: d,e thyroid, renal and liver panels, pregnancy test, CBC, and Vitamin B12 (C)	X				X						X
Suicidality, Patient Health Questionnaire (PHQ)-Item 9 (C)	X	X	X	X	X	X	X	X	X	X	X
Zucker Hillside Side Effects Form (C)	X				X						X
Total Time/Visit for Youth Questionsf (minutes)	15-20	5	5	5	15-20	5	7	5	7	5	15-20
Total Time/Visit for Caregiver Questionsf (minutes)	15-20	5	5	5	15-20	5	7	5	7	5	15-20

P= Caregiver; Y= Youth, C= Clinician. Kiddie-SADS-Present and Lifetime-PL 2013;

aKSADS will be performed at any time point after enrollment.

bBaseline fasting serum glucose is highly recommended, however, results within the past six months will be acceptable.

cItems from the PROMIS=Patient Reported Outcome Measurement Information System;

dAny labs completed within the past 6 months are acceptable except for pregnancy test;

At baseline a negative serum or urine pregnancy test is required in girls who have reached menarche prior to prescribing metformin.

eLabs are recommended, however these are not required to start or continue in the study.

fClinician and other assessments (e.g. labs, vitals) are part of a routine clinical visit and therefore, do not add time.

Our population will be  $\geq$ 85%ile BMI (weight of such 8- and 9 year-olds will likely be comparable to an average 10-year-old child); 2) MET has a favorable side effect profile; and 3) prior reports as well as the investigators' previous experiences with the safe and well-tolerated use of MET in patients  $\geq$ 8 years old. All patients will have a renal panel prior to starting MET to evaluate for renal impairment that would preclude use of MET.

Participants randomized to treatment with MET will start at a recommended dose of 500 mg orally at night and slowly titrated in 2-week intervals to ensure that each patient achieves maximum insulin-sensitizing effects of the drug while minimizing the chance of side effects (see Table 1). We selected 50kg as the weight at which we felt comfortable increasing to a maximum total daily dose of 2000mg (1000mg twice daily). These youth will be at a low-end adult-comparable weight. We anticipate that most participants  $\geq$ 10 years old will be  $>50$ kg, which is the 95%ile for weight for 10-year-olds of both sexes. Children  $<50$ kg, likely those patients  $<10$  years, will have a reduced maximum daily dose of 1500mg. If

patients exhibit untoward gastrointestinal side effects while taking MET, clinicians will have the option to switch to an equivalent dose of the once-daily extended-release form of MET, which may alleviate side effects. If a patient does not tolerate a specific dose, the clinician will also have the option of reducing that dose by 500mg/day to a minimum recommended daily dose of 500mg twice daily. At Week 8, the dose for the <50kg group may be titrated to the maximum of 2000mg/day (1000mg twice daily) if tolerated and strategy, in general, MET will be at steady-state target levels well before key outcomes are assessed at Month 6. We will also recommend that MET be taken with food to minimize side effects. If a participant's BMI percentile <5% (=underweight) his/her treatment with MET will be discontinued. Although the risk of low vitamin B12 while taking MET is associated with age > 50 years and having type II diabetes, we will monitor B12 levels and a CBC throughout study participation.

Clinicians and patients must be willing to be randomized to either treatment arm. However, the clinician may choose to initiate or continue (for those on a subtherapeutic dose) metformin at their clinical discretion regardless of randomization following a recommended initial 3 month period of treatment. These patients' data will be considered in a different analytic group regardless of randomization.

**Comparators:** Healthy Lifestyle Intervention (LIFE): This healthy lifestyle intervention (LIFE) consists of introducing participants and families to a healthy eating plan and physical activity. Prior to study initiation, study site staff will participate in a live (or taped) training session from a dietitian to become educated with LIFE. At baseline visit patients and caregivers will watch a standardized video about LIFE that was developed by [name] and his group. The video explains the concept of a Traffic Light Plan (TLP) that is a classification system for food and activity (GREEN, YELLOW, RED). This plan encourages participants to limit RED foods (high-calorie, low-nutrient) and RED activity (sedentary), replacing them with GREEN foods (low-calorie, high-nutrient) and GREEN activity (moderate-to-high intensity). Participants will also receive a Food Reference Guide and Activity Reference Guide, categorizing food and activities in the TLP framework that was adapted from the Healthworks! Youth Fitness 101 program developed specifically for overweight and obese children by [name]. The baseline session will include a brief discussion of diet and physical activity instruction. At least 150 minutes/week of physical activity will be recommended. A link to the LIFE video and all handouts will be available on the study websites at [www.mobilitystudy.org](http://www.mobilitystudy.org) and offers a standardized, home-based exercise component for patients. At follow-up visits, patients and caregivers will have the option to watch the video again, and study staff will briefly reinforce nutritional guidance, remind participants about the need for 150 minutes of physical activity/week, and be available to answer any general questions on healthy lifestyle habits. Prior studies indicate that 33% of youth will decrease BMI with this LIFE intervention.

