#### **A. SPECIFIC AIMS**

The specific aim of this study is to address the significant gap in the evidence base for metformin (MET) use in overweight and obese youth with Bipolar Spectrum Disorders (BSD).

The overall objective of this prospective, large, PRAGMATIC randomized trial is to study the impact of MET and healthy lifestyle intervention (LIFE) vs. LIFE alone on patient-centered outcomes of body weight, Second Generation Antipsychotics (SGA) adherence and satisfaction, psychiatric symptom burden (e.g. mood/anxiety), and quality of life (QoL). We will also examine metabolic outcomes.

**Specific Aim 1:** Assess the overall and subgroup-specific impact of MET+LIFE versus LIFE alone on short- (6mo) and long-term (24mo) **weight and metabolic health** in overweight and obese youth with BSD.

**H1.1:** Overall, assignment to treatment with MET will abrogate more weight gain and lead to fewer adverse metabolic outcomes than LIFE alone at 6 and 24 months.

**H1.2:** (Heterogeneity of Treatment Effects [HTE]): MET's effectiveness at abrogating weight gain and components of metabolic syndrome will vary with respect to the following factors (see Patient Population and Background for rationale and prior data): 1) Change in BMI z-score from SGA initiation to baseline (in patients already receiving SGA treatment); 2) Prior exposure to and duration of SGA treatment; 3) Baseline BMI z- score; 4) Baseline psychotropic weight burden (in SGA non-naïve patients; as defined in Measures below); 5) BSD as diagnosed by a structured interview; 6) Age; 7) Type of insurance (public/private); 8) Ethnicity (Hispanic/Non); 9) Baseline insulin resistance (HOMA-IR); 10) Race (African-American (AA) vs non-AA).

**Specific Aim 2:** Assess the overall and subgroup-specific impact of MET+LIFE vs. LIFE alone on short- (6mo) and long-term (24mo) **SGA adherence and treatment satisfaction**, including assessment of how these effects may be mediated by MET effects on weight gain.

**H2.1:** Overall, assignment to treatment with MET will lead to better SGA adherence and greater treatment satisfaction than LIFE alone after both 6 and 24 months.

**H2.2:** (HTE): MET effectiveness with regard to SGA adherence will vary with respect to: 1) Baseline weight acceptability; 2) Baseline psychotropic medication treatment acceptability; 3) Type of insurance (public/private).

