**H2.3:** The overall effects of MET treatment on SGA adherence will be mediated by degree of weight abrogation, and this relationship will be stronger among girls than boys. We anticipate a possibly complex relationship between abrogation of weight gain (associated with MET) and SGA adherence, because weight gain may also be avoided via SGA non-adherence (at the probable cost of sub-optimal psychiatric outcomes; see Specific Aim 3). A statistical framework (marginal structural models) to accommodate this possibility is described in the Statistical Analysis Plan.

**Specific Aim 3:** Assess the overall and subgroup-specific impact of MET+LIFE vs. LIFE alone on **psychiatric symptom burden, psychotropic treatment changes, and overall and weight-related QoL**, including assessment of how these effects are mediated by MET effects on weight gain and SGA adherence.

**H3.1:** Overall, assignment to treatment with MET will be associated with lower psychiatric symptom burden, decreased risk for symptom-driven treatment changes, and greater improvements in overall and weight-related QoL than LIFE alone at both 6 and 24 months, post-randomization.

**H3.2:** (HTE): MET effects on psychiatric symptoms will be smaller in patients who meet full DSM criteria for a BSD.

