for data entry and real time validation (e.g., automated data type and range checks); 2) HIPAA-compliant and 21 CFR Part 11-ready audit trails for tracking data manipulation and exports; 3) record locking and electronic signature functions; 4) control of view/edit rights; 5) a tool for reporting, monitoring and querying patient records; and 6) automated export to common statistical packages. REDCap is hosted on a network specially designed to support the rigorous security and compliance requirements of clinical research projects. Administered by the CCHMC Division of Biomedical Informatics, this network features multiple firewalls and a central facility for managing hosted systems and users, creating another layer of access control and audit capability on top of what REDCap already provides (e.g., user access can be monitored and controlled at the network level without making any changes within REDCap itself). These capabilities are available to authorized network administrators and REDCap study owners only, and user access changes are documented by an audit trail. The data management team will monitor the database throughout the study to assure that data are complete and accurate.

**Analyses of Specific Aims:** Each specific aim involves assessment of domains that are hypothesized to be affected by MET either directly or indirectly through other domains. Our approach to potential HTE distinguishes effect moderators from mediators of distal outcomes. Moderators include fixed patient characteristics and pre-treatment covariates values. Mediators include variables that are hypothesized to be affected by MET treatment and that may in turn affect other outcomes. We will utilize generalized linear mixed models (GLMM), which allow for outcomes from a range of distributions and will include random effects to account for unspecified causes of variation among sites and patients, and subgroup-specific coefficients to assess HTE.

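### The K-SADS diagnosis is a planned moderator (H1.2 item 5; the only one in H3.2), yet Table 2 lets the interview take place on treatment and no rule ties the diagnosis to baseline status

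*Combined protocol and SAP*

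**What the plan says.** Section A lists ten factors that may modify the effect on weight and metabolic outcomes (H1.2). The fifth is "5) BSD as diagnosed by a structured interview". For psychiatric outcomes, H3.2 names one factor and a direction: "MET effects on psychiatric symptoms will be smaller in patients who meet full DSM criteria for a BSD". It does not say whether the criteria are to be met currently or over the lifetime. H3.1 expects that "assignment to treatment with MET will be associated with lower psychiatric symptom burden".

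Section E.b, under Analyses of Specific Aims, separates two kinds of variable: "Moderators include fixed patient characteristics and pre-treatment covariates values", whereas "Mediators include variables that are hypothesized to be affected by MET treatment and that may in turn affect other outcomes".

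Section E.a describes the K-SADS-PL mood modules under Screening/Baseline Procedures and gives the assessment of heterogeneity as one purpose. Table 2 marks the interview only in the screening/baseline column, but footnote a to that row reads "KSADS will be performed at any time point after enrollment". Treatment is assigned at baseline ("once patients are randomized at baseline, MOBILITY is primarily an observational pragmatic study"), so the permitted period includes time on treatment.

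**The concern.** The footnote allows a variable that the analysis treats as pre-treatment to be measured after treatment has started. If metformin, weight change or a change in SGA adherence alters mood symptoms, a late interview classifies patients partly on the outcome of H3. Comparing the arms within such classes no longer compares randomized groups. H3.2 is most exposed, because the diagnosis is its only moderator and the outcome is psychiatric symptoms. For H1.2 the diagnosis is one factor among ten and the outcome is weight or metabolic status, so the link is weaker.

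A second, smaller matter is missing data. A patient who leaves before being interviewed has no class, and the plan gives no rule for this.

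**Working it through.** **1. Does another provision repair the timing?** None in the available text does.
- The Month 6 rule in section E.a governs when clinicians are told the diagnosis, not when the interview is held.
- Interviewers come from the coordinating centers and are separate from the clinical sites, but they are not said to be blind to arm.
- The marginal structural models in section E.b deal with changes in SGA regimen.
- There is no as-of-baseline rating rule, no use of the interview date and no rule for a missing K-SADS.

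**2. How large could the bias be?** The plan states no figure to reproduce, so this is an illustration. Every input below is an assumption.
- Baseline symptom score S0 ~ N(0,1), and A = 1 for MET, 0 for LIFE (1:1, as planned).
- Later score S6 = 0.6·S0 + 0.8·e - δ·A, with e ~ N(0,1). The true effect is -δ in every patient, so there is no true heterogeneity.
- Lifetime-type diagnosis: positive if S0 > 0, or if the interview is late and S6 > 0.
- Current-state diagnosis: positive if the score at the time of interview exceeds 0.
- Model: S6 - S0 = b0 + b1·S0 + b2·A + b3·D + b4·A·D. The effect is b2 in diagnosis-negatives and b2 + b4 in positives; b4 should be 0.

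Results (4 million simulated records per setting):

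| δ | Share late | Rating | % positive, LIFE / MET | Effect, negatives | Effect, positives | b4 |
|---|---|---|---|---|---|---|
| 0.2 | 0 | either | 50 / 50 | -0.200 | -0.200 | 0.000 |
| 0.2 | 25% | lifetime | 53.7 / 52.8 | -0.189 | -0.206 | -0.017 |
| 0.2 | 50% | lifetime | 57.3 / 55.5 | -0.170 | -0.204 | -0.033 |
| 0.2 | 100% | lifetime | 64.7 / 61.1 | -0.111 | -0.195 | -0.083 |
| 0.3 | 50% | lifetime | 57.4 / 54.7 | -0.257 | -0.308 | -0.052 |
| 0.3 | 100% | lifetime | 64.7 / 59.5 | -0.173 | -0.297 | -0.125 |
| 0.2 | 50% | current | 50.0 / 46.1 | -0.161 | -0.170 | -0.010 |
| 0.2 | 100% | current | 49.9 / 42.1 | -0.098 | -0.091 | 0.007 |

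With a lifetime-type rating, the effect looks larger in diagnosed patients. H3.2 predicts a smaller one, so the bias works against the hypothesis. With a current-state rating, the interaction stays near zero and both subgroup effects shrink. With all interviews before treatment, there is no bias.

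Two limits apply. First, the cut at zero implies many new diagnoses: in LIFE, (64.7 - 50)/50 = 29% of baseline-negatives convert. Second, the model omits the baseline-by-MET term that the plan adds for its HTE analyses. Refitting with that term kept the sign of the lifetime-type bias and made it somewhat larger, so the range is not an upper limit.

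**3. How many patients could lack a class?** If no leaver had been interviewed first, the count is 1800 × loss, and the standard error of the interaction grows by 1/√(1 - loss).
- The plan's retention of about 90% (section F.f): 1800 × 0.10 = 180; 1/√0.90 = 1.05.
- Dropout of 24% (MET) and 28% (control) in the earlier NIMH-supported trial (section C): 432 and 504; factors 1.15 and 1.18.

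These are ceilings.

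**The case against.** The strongest reply is that the instrument covers lifetime as well as present diagnosis and serves to check whether a clinical diagnosis meets research criteria. Metformin cannot undo a lifetime diagnosis already met, so the variable is close to a fixed characteristic. Only new episodes after randomization can change the class. If 5% of baseline-negatives convert, with all interviews late and a true effect of -0.30 SD, one calculation gives -0.28 in negatives and -0.31 in positives. At 20% conversion it gives -0.26 and -0.31. This stands as an argument that the bias may be small. It does not show that it is nil, and the figures depend on how closely conversion follows symptoms: tying conversion wholly to the later score gave larger values at the same rates, with the same sign. Nor does H3.2 say that the lifetime rating is the one to be used.

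It is also fair that the table and section E.a place the interview at baseline, so most interviews may in fact be early. The documents give no count either way.

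On missing data, the reply largely succeeds. A reader might infer that early leavers never receive a class. The footnote does not imply that, since an interview soon after enrollment is allowed; only patients who leave before being interviewed lack one. Those who leave before Month 6 also lack the Month 6 outcome, so earlier interviewing would recover little for that analysis.

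**Conclusion.** The inconsistency is real: footnote a allows a planned moderator to be measured in a way that fails the plan's own definition of a moderator, and nothing in the available text corrects it. Parts of the document, including whatever stood between sections C and E, were not available, so a rule placed there cannot be excluded.

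The consequence is possible bias in the subgroup effects and in the treatment-by-diagnosis interaction, chiefly for H3.2. With a lifetime-type rating, true effects of -0.2 to -0.3 SD and half to all interviews late, the illustrative interaction bias is about -0.03 to -0.13 SD. It is smaller with fewer late interviews. With a current-state rating, the harm is shrinkage of both subgroup effects.

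Three stronger readings are tempting but not supported:
- A reader might infer that a fixed share of the subgroup effect, such as 20-29%, will be lost. That size needs a current-state diagnosis, a strong assumed correlation with symptoms and every interview near Month 6. The documents establish none of these.
- A reader might infer that late interviews would create false support for H3.2. In the lifetime-type calculations the bias runs the other way and could mask the predicted difference.
- A reader might infer that the main result is at risk. The overall comparisons, including the primary BMI z-score, do not use the K-SADS.

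The change is worth making because it is cheap and a named hypothesis rests on this variable.

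**What to change.** 1. In the analysis plan, define the moderator for H1.2 item 5 and H3.2 as full BSD criteria met with onset dated before randomization, whenever the interview takes place. This keeps post-randomization episodes out of the moderator.
2. Amend footnote a so that the interview is aimed for at or before randomization where feasible. A Month 1 limit would not meet the plan's own definition, since metformin may already have been started by then.
3. Record the interview date, and state how patients without a K-SADS are handled.
4. Repeat the HTE analysis in patients interviewed at or near baseline.

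The cost is a few sentences, one date field and one sensitivity analysis, with slight scheduling pressure on the central interviewers. Onset dated from memory will carry some recall error, which could differ by arm because patients know their treatment; step 4 is the check on that. Making the interview compulsory before randomization for all 1800 families would be cleaner, but it is harder to justify in a trial designed to avoid study-specific scheduling, and the definition in step 1 does not depend on it.
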